## **6.2 Exclusion Criteria**

The patient may not enter the trial if ANY of the following apply:

- 6.2.1 Has taken nabiximols, cannabis, or a cannabis-derived product for medicinal or recreational purposes in the 30 days prior to Visit 1 or unable to abstain for the duration of the study.
- 6.2.2 Did not tolerate or did not respond adequately to treatment with nabiximols or another cannabis-based medication if exposed at any time before the 30-day period prior to Visit 1.
- 6.2.3 Any concomitant disease or disorder that has spasticity-like symptoms or that may influence the patient's level of spasticity.
- 6.2.4 Medical history suggests that relapse/remission is likely to occur during the trial, which, in the opinion of the investigator, is expected to influence the patient's spasticity.
- 6.2.5 Has had a relapse of MS within the 60 days prior to Visit 1.
- 6.2.6 Currently using botulinum toxin injection for the relief of spasticity (within 6 months of Visit 1) or is unwilling to abstain for the duration of the trial.
- 6.2.7 Currently taking antipsychotic medication.
- 6.2.8 Currently taking benzodiazepines unless doses and dosing regimen have been stable for at least 30 days prior to Visit 1.
- 6.2.9 Clinically suspected to have a contracture in one of the muscle groups of the lower limbs, preventing assessment with the MAS.
- 6.2.10 Has any known or suspected hypersensitivity to cannabinoids or any of the excipients of the IMP.
- 6.2.11 Has experienced myocardial infarction or clinically significant cardiac dysfunction within the last 12 months prior to Visit 1 or has a cardiac disorder that, in the opinion of the investigator, would put the patient at risk of a clinically significant arrhythmia or myocardial infarction.
- 6.2.12 Has a diastolic blood pressure of < 50 mmHg or > 105 mmHg or systolic blood pressure < 90 mmHg or > 150 mmHg (when measured in a sitting position at rest

for 5 minutes) or a postural drop in the systolic blood pressure of > 20 mmHg at Visit 1 or Visit 2. All measurements will be performed singly and can be repeated once, if any are outside the reference range but not considered clinically significant.

6.2.13 Has clinically significant impaired renal function at Visit 1, as evidenced by an estimated creatinine clearance lower than 50 mL/min. All measurements will be performed singly and can be repeated once, if any are outside the reference range but not considered clinically significant.

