^b A comprehensive physical examination, including an assessment of height, will be completed at Screening (Visit 1) only; subsequent physical examinations will be symptom-directed.

^c Serum pregnancy test at Visits 1 and 10; urine pregnancy test at Visits 2 and 6 (pre-dose).

^d On the day before PK blood sampling at Visits 4, 5, 8, and 9, patients will be prompted to record whether they started their morning and evening doses of IMP within 30 minutes of a snack or meal. On the day of PK blood sampling, the exact time and date of PK blood sampling and the time of the patient's snacks and meals should be recorded for the PK blood sampling schedule (see [Table 8.1-3](#)). Please note that more than one PK sample may be collected at distinct time points during a single visit.

^e Patients will record their 11-point NRS spasticity score, spasm count, and use of antispasticity medications in an electronic diary once daily, around the same time each day, preferably in the evening before retiring to sleep, for at least 7 days prior to Visits 2 and 6 and throughout the trial until Visit 9. Investigational medicinal product dosing will be recorded by the patient in an electronic diary from Visits 2 through 9.

^f MAS assessments will occur at Visit 1 (Screening) and at scheduled time points before (Visits 2 and 6 [pre-dose]) and after (Visits 2, 5, 6, and 9 [3 hours \pm 15 minutes post-dose]) IMP administration; for Visits in which the morning dose consists of more than 1 spray (Visits 5 and 9), post-dose assessments will occur 3 hours \pm 15 minutes after the first spray of the morning dose.

^g Non-ambulatory patients are not expected to perform the T25FW test.

^h IMP administration of the morning dose will occur at the trial site within 30 minutes after a standardized snack containing at least 300 kcal (of which approximately 30 kcal is composed of fat) under the supervision of site staff. On the days of scheduled MAS assessments other than Visit 1, patients who are taking antispasitic therapy should take their regular morning dose at least 1 hour before administration of IMP; IMP will not be administered in the evening of Days 21 and 51.

ⁱ In cases where patients are not able to attend study visits due to special circumstances (e.g., COVID-19 pandemic), the investigator will discuss with the Sponsor potential mitigation approaches for IMP dispensing, secure delivery, and collection.

Table 8.1-3 Pharmacokinetic Blood Sample Schedule

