10.1.3 Target Days and Visit Window

Visit windows are summarized in [Table 10.1-3](#) for efficacy data and urine drug screen collection and, in [Table 10.1-2](#) for all other safety endpoints.

When there are multiple observations within a visit window, the value closest to the target day will be analyzed (as described in [Table 10.1-1](#)).

For safety assessments, on-treatment assessments will be preferred to off-treatment ones.

In case of ties between observations located on different sides of the target, the observation with the earliest date/time will be used. In case of ties between observations located on the same side of the target, (i.e., more than one value for the same day but at different time), the observation with the earliest date/time will be used. However, in case of non-respect of wash-out period, the one done at least 7 days after last Period 1 dosing date will be preferred.

For efficacy, PRO endpoints visit windowing will apply whether patient is on or off treatment.

Table 10.1-1 Longitudinal Assessment – Analysis Day and Target Day

Treatment Period	Visit / Day	Analysis visit	Target Day (defined by period)	Observation used for analysis, if more than one exists
Screening	Visit 1 / Day -28 to -1	Screening	Day -28 to -1	Latest value
Period 1	Visit 2 / Day 1	Day 1	Day 1*	Closest to Target Day But Day 1 H0 should be before 1 st IMP intake and Day 1 H3 should be post IMP intake
	Visit 3 / Day 8	Day 8	Day 8	Closest to Target Day
	Visit 4 / Day 15	Day 15	Day 15	Closest to Target Day
	Visit 5 / Day 21	Day 21	Day 21	Closest to Target Day
Period 2	Visit 6 / Day 31	Day 1	Day 1*	Closest to Target Day But Day 1 H0 should be before 1 st IMP intake and

				Day 1 H3 should be post IMP intake.
	Visit 7 / Day 38	Day 8	Day 8	Closest to Target Day
	Visit 8 / Day 45	Day 15	Day 15	Closest to Target Day
	Visit 9 / Day 51	Day 21	Day 21	Closest to Target Day
Follow-up	Visit 10 / Day 58	Day 28	Day 28**	Closest to Target Day

H = Hours; IMP = Investigational medical product.

** Day 1 is based on the date of IRT call within each period*

*** Day 28 relative to the period where IMP is permanently discontinued thus visit is expected between Day 25 and Day 31*

Table 10.1-2 Longitudinal Assessment – Target Day and Visit Window – Part 1

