	Visit 5 / Day 21	Day 21***		Day 19 up to LP1V	Day 19 up to LP1V	Day 1 post dose of 1 st IMP intake up to LP1V	Day 1 post dose of 1 st IMP intake up to LP1V
Wash out period							
Period 2	Visit 6 / Day 31	Day 1H0*		Day 1 – 4 days to D1H0 *	Day 1H0 (before P2 IMP intake)	Day 1H0 (before P2 IMP intake)	Day 1H0 (before P2 IMP intake)
	Visit 6 / Day 31	Day 1H2- H4**			Day 1 post dose (the day of 1 st P2 IMP intake)** up to Day 18		
	Visit 8 / Day 45	Day 15		Day 2 (day following IMP intake) – Day 18 (or the first day of maintenance phase)			
	Visit 9 / Day 51	Day 21***		Day 19 to LP2V	Day 19 to LP2V	Day 1 post dose of Period 2 1 st IMP intake up to LP2V	Day 1 post dose of Period 2 1 st IMP intake up to LP2V
Follow-up	Visit 10 / Day 58	Day 28****		After last IMP dosing			

H = Hours, P = Period; LP1V = Last visit during Period 1, LP2V = Last visit during Period 2, IMP = Investigational Medicinal Product, NRS = Numerical Rating Scale; IRT = Interactive Response System, MAS = Modified Ashworth Scale, MSSS-88 = Multiple Sclerosis Spasticity Scale; T25FW = Timed 25-Foot Walk.

* Day 1 is based on the date of IRT call within each period.

** D1H2-H4 for sensitivity analysis purpose only assessments collected between at H3 (+/- 15 min) post first IMP morning spray will be considered. Should be collected during the titration phase

*** Day 21 should be collected during the maintenance phase (including off-treatment days).
 **** Day 28 relative to the period where IMP is permanently discontinued.

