10.2 Baseline

For patient electronic diary-based endpoints (NRS-spasticity and spasm count, respectively), baseline is defined as the weekly average of daily electronic diary entries over the last 7 days prior to randomization (Visit 2, Period1 Day 1H0).

In case of missing assessments within the 7 days preceding Period1 Day1 H0

For 11-point NRS spasticity scale, the weekly average will be set to missing if scores are missing for 4 days in total or for 3 consecutive days within the 7-days period.

For daily spasm count, the weekly average will be derived as detailed in [Section 10.19](#)) and will be set to missing if spasm count is not collected during 4 days out of 7 or for 3 consecutive days during the last 7 days preceding Day 1H0.

For clinic-efficacy based endpoints, baseline is defined as the last record or measure collected prior to the first dose of IMP in each treatment period.

However, if deemed necessary the baseline will be defined for each period as described in [Section 10.1.2](#) as:

the reference day for Period 1,

the reference day for Period 2,

For clinic-safety based endpoints, baseline is defined as the last record or measure collected prior to the first dose of IMP or if deemed necessary as the reference day as described in [Section 10.1.2](#).

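### The SAP's earliest-of-the-day tie rule can pass over the 3-hour post-dose MAS at Visits 5 and 9, and it conflicts with the last-pre-dose baseline

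*SAP*

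**What the plan says.** SAP 10.1.3 selects one record per analysis visit. The first criterion is calendar distance: "When there are multiple observations within a visit window, the value closest to the target day will be analyzed". For ties on the same side of the target it adds ("i.e., more than one value for the same day but at different time), the observation with the earliest date/time will be used"). The section covers efficacy as well as safety.

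Table 10.1-1 qualifies this for the Day 1 rows of both periods: "But Day 1 H0 should be before 1 st IMP intake and Day 1 H3 should be post IMP intake". The Day 21 rows, which stand for Visits 5 and 9, have only the nearest-day criterion. For Screening, the same table asks for the latest value. In Table 10.1-3 the Period 1 MAS window for Day 21 is "Day 19 up to LP1V", where LP1V is the last visit of Period 1. Its footnote requires the maintenance phase and gives no time after dose.

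The timing of the endpoint MAS is set elsewhere. Footnote f of SAP Table 8.1-2 states: "for Visits in which the morning dose consists of more than 1 spray (Visits 5 and 9), post-dose assessments will occur 3 hours", with a ±15 minute tolerance, counted from the first spray. Protocol 9.1.2.3 and 9.1.4.3 agree.

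On baseline, SAP 10.2 says for clinic efficacy endpoints: "baseline is defined as the last record or measure collected prior to the first dose of IMP in each treatment period". Protocol 13.4 has the same rule for all clinic-based endpoints. SAP 10.2 has a separate sentence for clinic safety endpoints, which also takes the last record before the first dose.

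**The concern.** A tie rule operates only when there are duplicates, so it should pick the right record in exactly those cases. At Day 21 and Day 51 this one does the reverse whenever the extra MAS comes first. A pre-dose assessment done out of habit, as at Visits 2 and 6, or an assessment done too early and then repeated on time, would replace the protocol-defined score although that score is in the database. The dose-time condition written for Day 1 H3 is missing from the time point that carries the primary inference.

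For baseline, two programmers following two sections of the same SAP could derive different values, and so different changes from baseline. The SAP addendum keeps inferential analysis of LLMT-6 and reporting of vital signs as in the SAP, and it leaves the windowing rule unchanged.

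**Working it through.** **1. Endpoint visit (Visit 5 or 9), two MAS on the same day.** Let A be pre-dose or too early, and B be at 3 hours ±15 minutes after the first spray.

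- Distance to the target day: equal, because only days count.
- Same-day tie: the earliest wins, so A is analysed and B is dropped.
- Other safeguards: the dose-time condition in Table 10.1-1 covers Day 1 only. The ±15 minute filter in the footnote to Table 10.1-3 and the time-window analysis in SAP 12.5.4.3.3 cover Day 1 H3 only. The major deviation list in SAP Appendix 1 has no item for a mistimed Day 21 MAS.

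A mistimed value later than B would not be selected. A sole mistimed value would be used whatever the tie rule said.

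**2. Baseline (Day 1 H0), two pre-dose values on the same day.**

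| Source | Value taken |
|---|---|
| SAP 10.1.3 tie rule | first |
| SAP 10.2 and Protocol 13.4 | last |

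The Day 1 condition in Table 10.1-1 keeps pre-dose and post-dose values apart but does not choose between two pre-dose values.

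The repeat that the documents foresee here is blood pressure at Visit 2. Protocol 6.2.12 says "All measurements will be performed singly and can be repeated once" if out of range but not considered clinically significant. Assumed example: first systolic reading 155, repeat 145 mmHg (the limit is 150). The tie rule gives a baseline of 155 and 10.2 gives 145, so every later change differs by 155 − 145 = 10 mmHg. SAP Appendix 6 flags a high systolic value only if it exceeds 180 and has risen by at least 20. From 155, a value of 181 is already a rise of 26, so in this example the flag is the same under either baseline. It can depend on the choice only if one of the readings exceeds 180 − 20 = 160.

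**3. Size for the primary endpoint, illustration only.** Planning inputs (SAP 8.2, SAP 12.0): difference −0.18, SD of paired differences 0.71, two-sided 5%, 90% power, 170 completers.

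- Reproduction: a paired t-test with the noncentral t distribution needs n = 166 for 90% power. At n = 170 the noncentrality is 0.18 × √170 / 0.71 = 3.31 and power is 90.8%. This agrees with the plan.
- Dilution: let f be the share of nabiximols Day 21 scores replaced and r the share of the effect absent from the replacing score. The difference becomes 0.18 × (1 − f × r), with the SD held at 0.71. Neither f nor r is in the documents.

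| f | r | Difference (absolute) | Power at n = 170 |
|---|---|---|---|
| 0 | – | 0.180 | 90.8% |
| 1% | 50% | 0.1791 | 90.5% |
| 5% | 50% | 0.1755 | 89.3% |
| 5% | 100% | 0.171 | 87.7% |
| 10% | 50% | 0.171 | 87.7% |
| 10% | 100% | 0.162 | 84.1% |

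**The case against.** The protocol schedules exactly one MAS at Visits 5 and 9 and no pre-dose MAS there, and nothing provides for repeating a MAS. With one record per visit the tie rule never operates on the primary endpoint. This stands, and it is why the expected effect is small. It does not make the rule right when an unscheduled record exists.

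SAP 10.2 is the dedicated baseline definition, and SAP 12.2 repeats it. A specific definition would normally prevail over a general tie rule. This is a fair reading and probably the intended one. But 10.1.3 does not exempt baseline, and Table 10.1-1 asks for the latest value at Screening and not at Day 1.

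The rule is fixed in advance, blind to outcome and the same for both treatments. This also stands: it would be expected to dilute the contrast, and no inflation of type I error is shown.

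A reader might also infer that an off-drug MAS a day or more after an early Visit 5 could displace the on-drug one, since SAP 10.1.3 says: "For efficacy, PRO endpoints visit windowing will apply whether patient is on or off treatment". The documents do not support this. The window closes at the last Period 1 visit, the maintenance phase ends no later than the Visit 5 date (SAP 10.8.1), and washout follows that morning's dose (Protocol 8.2 and 9.1.3). A later MAS is therefore not clearly in the window. Using off-treatment values for patients who stopped early also follows from the treatment-policy strategy in SAP Table 9.1-2.

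**Conclusion.** The point holds in limited form. For Day 21 and Day 51, the written rule selects the wrong MAS whenever an earlier extra one exists on the visit day. For pre-dose Day 1 and Day 31 records, it conflicts with the baseline definition without a stated precedence. Blood pressure at Visit 2 is the foreseeable case; a MAS baseline conflict would need two unplanned pre-dose assessments on one day.

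The conclusion rests on the text and not on the power figures. A reader might take those figures as an expected loss, but they are not one: f and r are assumed, complete loss of effect before the morning dose is the extreme case, and 170 completers is no longer the operative number, because the addendum records that enrolment was halted short of plan. The true effect may be nil. The point is worth correcting because it concerns which value enters the primary analysis and can be settled in advance at little cost.

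**What to change.** Add to SAP 10.1.3:

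- **(a)** For Day 1 H0 of each period, use the last value before the first dose of that period, as in 10.2; the same-day tie rule does not apply.
- **(b)** For MAS at Day 1 H3, and at Day 21 of each period in patients dosed that morning, use the same-day post-dose value closest to 3 hours after the first morning spray.

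The cost is SAP wording and minor programming. SAP 12.5.4.3.3 already needs the MAS time relative to the first spray for Day 1 H3. Part (b) assumes that the same times are recorded at Visits 5 and 9. A blinded count of patient-visits with more than one MAS would show whether the change affects any record.

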10.2 Baseline

For patient electronic diary-based endpoints (NRS-spasticity and spasm count, respectively), baseline is defined as the weekly average of daily electronic diary entries over the last 7 days prior to randomization (Visit 2, Period1 Day 1H0).

In case of missing assessments within the 7 days preceding Period1 Day1 H0

For 11-point NRS spasticity scale, the weekly average will be set to missing if scores are missing for 4 days in total or for 3 consecutive days within the 7-days period.

For daily spasm count, the weekly average will be derived as detailed in [Section 10.19](#)) and will be set to missing if spasm count is not collected during 4 days out of 7 or for 3 consecutive days during the last 7 days preceding Day 1H0.

For clinic-efficacy based endpoints, baseline is defined as the last record or measure collected prior to the first dose of IMP in each treatment period.

However, if deemed necessary the baseline will be defined for each period as described in [Section 10.1.2](#) as:

the reference day for Period 1,

the reference day for Period 2,

For clinic-safety based endpoints, baseline is defined as the last record or measure collected prior to the first dose of IMP or if deemed necessary as the reference day as described in [Section 10.1.2](#).

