##### **9.1.4.1 Visit 6 (Day 31)**

Visit 6 will occur 30 days after the first dose of IMP. A visit window of  $\pm 1$  day from the scheduled visit date is permitted, but it is preferred that the visit is performed on the scheduled visit day, where possible.

The following assessments/procedures will be performed on Day 31 predose:

- Concomitant medications review
- AE review
- Examination of oral mucosa
- Body weight measurement
- Vital signs measurement
- Urine pregnancy test (if appropriate)
- PK blood sampling for IMP ([Section 9.2.12.1](#))
- MAS assessment
- T25FW test
- C-SSRS assessment
- IMP dispensing

Following predose assessments and IMP dispensing, patients will administer a single dose of IMP with a standardized snack containing at least 300 kcal (of which approximately 30 kcal is composed of fat) at the trial site under the supervision of site staff.

The following assessments/procedures will be performed 2 to 4 hours postdose:

- MAS assessment (3 hours  $\pm 15$  minutes postdose)
- AE review
- Vital signs measurement

- PK blood sampling for IMP ([Section 9.2.12.1](#))

The patient will be provided dosing instructions and advised to contact the investigational site when in doubt about changes in the daily dose of IMP. The patient will be instructed to record IMP doses administered in the patient electronic diary.

The exact time of PK blood sampling and the time of the patient's snacks and meals should be recorded.

Following Visit 6, patients will titrate their daily dose of IMP for approximately 14 days until they achieve an optimized dose with an approximately 15-minute interval between sprays; patients should divide doses greater than 1 spray/day into a morning dose and an evening dose. Administration of the morning and evening doses of IMP should be maintained around the same time each day in a consistent manner in relation to food consumption, i.e., within 30 minutes after starting a snack or meal.

Patients should be reminded to record their 11-point NRS spasticity score, spasm count, and use of antispasticity medications in the electronic diary once daily, around the same time each day, preferably in the evening before retiring to sleep. In addition, on the day before Visits 8 and 9, patients will be prompted to record whether they started their morning and evening doses of IMP within 30 minutes of a snack or meal.

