## **13.4 General Considerations**

Unless stated otherwise, continuous variables will be summarized showing the number of non-missing values (n), mean, SD, median, minimum, and maximum. Categorical variables will be summarized showing the number and percentage of patients falling in each category.

For patient electronic diary-based endpoints, baseline is defined as the average of the last 7 days of electronic diary entries prior to randomization (Visit 2).

For clinic-based endpoints, baseline is defined as the last record or measure collected prior to the first dose of IMP in each treatment period.

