### **13.6.6 Safety**

The safety endpoints are listed below and will be compared with placebo as detailed in the following subsections:

- Frequency of TEAEs
- Change from baseline to each assessment time point by treatment period for the following:
  - Clinical laboratory parameters
  - Vital signs
  - Physical examination procedures
  - 12-Lead ECGs
- Columbia-Suicide Severity Rating Scale (C-SSRS) will be summarized at screening, and at each subsequent time point with reference to the last assessment (since last visit)

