6.2 Changes from Protocol

Table 6.2-1 Change from Protocol

Section of SAP Affected	Type of Change	Rational
Section 9.6.2.3,Section 11.0 and Section 12.5	Change to the definition of the Full Analysis Set (FAS) that is detailed in Protocol Section 13.3	
The FAS includes all patients who have taken a dose of investigational medicinal product (IMP). Per our specified estimand, patients should continue Period 1 despite stopping IMP. Hence, if a patient withdraws from the study, they should be handled as a missing data problem and will be imputed per this analysis plan.
 
Since IMP was taken, withdrawal may have been due to IMP and hence it may be important to include this patient in the analysis.

Section 7.3,Section 9.1,Section 10.15 and Section 12.5	Addition of an exploratory objective/ endpoint, the Lower Limb Muscle Tone-10 to those presented in Protocol Section 2 and Section 13.6.2	Since hip flexors and hip adductors are being collected the Lower Limb Muscle Tone-10 was added as exploratory endpoints

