10.1.2 Reference Day and Study Day

The reference day (Day 1) will be the day of the first dose of study drug administration.

For a patient who was randomized but not exposed, the reference day date will be imputed by the randomization date.

The reference day for Period 1 (Period 1 Day 1) will be the reference day.

The reference day for Period 2 (Period 2 Day 1) will be the first day of IMP administration during Period 2. For a patient who entered the second period but was not exposed during this period, this reference day date will be imputed by the date of Visit 6 IRT call, if any, or the Visit 6 date.

The study day is defined relative to the reference day date. For assessments that occur after this visit date, the study day is calculated as (assessment date – reference day date + 1). For assessments that occur prior to first dose date, study day will be calculated as (assessment date – reference day date).

For the analyses being done by treatment arm, an **analysis day** will need to be derived for each treatment period as described in Table 10.1-1. The analysis day is defined relative to the date of reference day of each study period.

For assessments that occur prior to reference day date, analysis day will be calculated as (assessment date – reference day date);

For assessments that occur on or after the Period 1 reference day date until the end of the wash-out period, analysis day will be calculated as (assessment date – Period 1 reference day date +1);

For assessments that occur on or after Period 2 reference day date the analysis day will be calculated as (assessment date – Period 2 reference day date +1);

Thus, there is no study day or analysis day referring to Day 0.

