12.7.4 Vital Signs

Vital signs will include sitting SBP and DBP and pulse rate which are planned to be measured at Day 1 H0, Day 1 H3, Day 15 and Day 21 of each treatment period as well as during the screening and the FU visit.

Vital signs parameters will be summarized on the Safety Analysis Set as described below.

Observed and change from baseline value in vital signs measures at each scheduled timepoint (Day 1 H3, Day 15, Day 21) will be summarized by treatment arm.

The number and percentage of patients with any clinically significant abnormal value and change in vital signs (as defined in [Appendix 6 Abnormality Criteria](#)**Error! Reference source not found.**) within each treatment period will be summarized by treatment arm within the Safety Analysis Set.

Observed and change from baseline (Screening) to FU will also be summarized by treatment sequence.

All vital signs data will be listed.

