12.7.5 Physical Examination, ECGs and other Observation Related to Safety

12.7.5.1 Physical Examination: Weight and BMI

Weight is planned to be measured at Screening, Day 1 H0 of each period and at follow-up visit.

Based on the Safety Analysis Set, weight and BMI (as defined in [Section 10.11](#)), observed and change from baseline value at each scheduled timepoint (Period 2 Day 1 H0, Day 21) will be summarized by treatment arm.

Observed and change from Screening to FU will also be summarized by treatment sequence.

The number and percentage of patients meeting a clinically significant change in weight (as defined in [Appendix 6 Abnormality Criteria](#) at any time during within each treatment period will be summarized by treatment arm. All measurements (scheduled or unscheduled) will be used to determine if any abnormality criteria is met (as determined in [Appendix 6 Abnormality Criteria](#)).

Weight and BMI will be listed.

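### SAP 10.2 drops the period-level baseline for clinic safety measures, contrary to Protocol 13.4 and without declaring the change

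*SAP*

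**What the plan says.** **Protocol.** Section 13.4 gives one rule, without separating efficacy from safety: "For clinic-based endpoints, baseline is defined as the last record or measure collected prior to the first dose of IMP in each treatment period". Section 13.6.6 frames the safety endpoints the same way: "Change from baseline to each assessment time point by treatment period for the following".

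**SAP 10.2.** The clinic-efficacy paragraph repeats the period-level rule and names a reference day for each period. The clinic-safety paragraph that follows has neither. Baseline there is "the last record or measure collected prior to the first dose of IMP or if deemed necessary as the reference day", with a pointer to SAP 10.1.2. That section uses the unqualified term for the first dose in the study, and then adds: "The reference day for Period 2 (Period 2 Day 1) will be the first day of IMP administration during Period 2".

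**SAP 6.2.** Table 6.2-1 has two entries: "Change to the definition of the Full Analysis Set (FAS) that is detailed in Protocol Section 13.3", and the addition of LLMT-10. Baseline is not mentioned.

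**Data available.** Protocol 9.1.4.1 opens its Visit 6 list with "The following assessments/procedures will be performed on Day 31 predose". The list includes vital signs, body weight, oral mucosa and C-SSRS, but no ECG or clinical laboratory sample.

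**SAP safety sections.**
- Vital signs (12.7.4): "Observed and change from baseline value in vital signs measures at each scheduled timepoint (Day 1 H3, Day 15, Day 21". Day 1 H0 is measured in each period but is not a change timepoint.
- Weight (12.7.5.1): "change from baseline value at each scheduled timepoint (Period 2 Day 1 H0, Day 21) will be summarized by treatment arm".
- C-SSRS (10.23, 12.7.5.3): emergence is an increase from baseline. Screening is excluded for ideation, and the Period 2 baseline is not given.
- Laboratory data and ECG (12.7.3, 12.7.5.2): Screening is named as baseline.

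**Addendum 7.0.** After early termination, vital signs and C-SSRS are still reported as the SAP sets out.

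**The concern.** The safety tables are presented by treatment arm, and each patient contributes one period to each arm. With a single baseline before Period 1, a Period 2 change includes whatever happened during Period 1 and the washout. A shift that begins on one treatment and persists is then counted again under the other. This reaches the mean changes, the Appendix 6 blood-pressure and pulse flags (which need both a value and a change criterion) and treatment-emergent suicidal ideation. The fallback in 10.2 does not settle the matter: it is discretionary, has no criterion and names no period. Two programmers could follow the text and produce different Period 2 tables, with no declared departure to tell a reader which rule was used.

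Three smaller faults lie in the same sections:
- Protocol 9.2.10 takes supine then standing readings at Visit 1 and sitting readings afterwards. Exclusion 6.2.12 uses a sitting reading at Visits 1 and 2, and SAP 12.7.4 describes the Screening reading as sitting. The Screening-to-follow-up change may therefore mix postures.
- SAP 12.2.3 defines orthostatic values as supine minus standing, so a fall is positive, but the flags are set at ≥ -20 (SBP) and ≥ -10 (DBP).
- SAP 12.7.5.1 summarises a Day 21 weight change, although weight is scheduled only at Visits 1, 2, 6 and 10.

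**Working it through.** The plan gives no figure to reproduce. The main finding is the comparison of texts above; the arithmetic only sizes it. Means, SDs and correlations are assumptions, because the documents give none.

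**1. Both directions are possible.** The low-SBP flag needs SBP < 90 and a decrease ≥ 20 mmHg. Illustrative readings:

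| Day 1 H0 | Visit 6 pre-dose | Visit 6 H3 | Change from Day 1 | Change from Visit 6 |
|---|---|---|---|---|
| 112 | 96 | 88 | -24, flagged | -8, not flagged |
| 100 | 112 | 88 | -12, not flagged | -24, flagged |

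**2. Size of the low-SBP flag at Period 2 H3.** Let X3 be the H3 value and X0 the baseline, bivariate normal with common mean, common SD, correlation ρ and no treatment effect. The flag probability is P(X3 < 90 and X3 - X0 ≤ -20). The SD of the change is SD·√(2(1-ρ)), and its correlation with X3 is √((1-ρ)/2).

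Central case: mean 125, SD 15, so the value criterion is z = (90 - 125)/15 = -2.33.
- From Visit 6, ρ = 0.8: SD of change = 15·√0.4 = 9.49, correlation √0.1 = 0.316, joint probability **0.09%**.
- From Day 1, ρ = 0.6: SD of change = 15·√0.8 = 13.42, correlation √0.2 = 0.447, joint probability **0.36%**.
- In 170 completers: 0.15 against 0.62 expected flags, a difference of about half a patient.

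Range: mean 120 to 130, SD 12 to 18, ρ 0.7 to 0.9 from Visit 6 and 0.5 to 0.7 from Day 1. The rates are 0 to 1.2% and 0.01 to 2.2%, a difference of 0 to 2.1 points. Simulated discordance between the two rules, with Day 1 H0 equally correlated with both Visit 6 readings, is 0.009 to 2.21% of patients, at most 0.0221 × 170 = 3.8. For low pulse (< 50 bpm and decrease ≥ 10; mean 70 to 80, SD 8 to 12) the rates are 0 to 1.8% and 0 to 2.8%.

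**3. Mean changes.** Suppose both sequences drift by D between Day 1 and Visit 6. A single baseline adds D to every Period 2 change. About half of each arm's observations come from Period 2, so each arm mean moves by about D/2 and the arm difference by about 0.

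**4. C-SSRS.** Suppose ideation scores are 0 at Day 1 H0, 2 at Period 1 Day 21, 2 at Visit 6 and 2 at Period 2 Day 15. From Day 1 the change is +2 in both periods, so ideation counts as emergent in both arms. From Visit 6 the Period 2 change is 2 - 2 = 0, so it counts only in the Period 1 arm.

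**5. Orthostatic flags as written.** With X = supine minus standing:
- SBP: P(X ≥ -20 given X ≤ 20), the cut at 20 reflecting exclusion 6.2.12; mean 0 to 10, SD 8 to 12: 95 to 100%.
- DBP: P(X ≥ -10); mean -5 to 5, SD 6 to 10: 69 to 99%.

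The flags would be met by most patients, which cannot be the intention.

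**The case against.** A reader might infer that the SAP contradicts itself, with vital signs on a period baseline and weight on a single one. The documents do not support that. Visit 6 pre-dose is the only scheduled weight after Period 1 treatment and before Period 2 dosing. Listing it as a change timepoint therefore fits a Visit 2 to Visit 6 change for Period 1 as well as it fits a single baseline. For C-SSRS the Period 2 baseline is undefined, not contradictory. For vital signs the SAP mostly points one way: 12.7.4 omits Day 1 H0 as a change timepoint, and 10.1.2 gives each period its own reference day and analysis day. What remains is a gap in 10.2, which still departs from the protocol as worded.

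Nor should one infer that every safety measure needs a period baseline. Laboratory data and ECG have no Visit 6 value, so the literal protocol rule would take the on-treatment Visit 5 value for Period 2. Screening is a sensible choice there; its only fault is that it is undeclared.

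The reference-day clause need not go. SAP 10.1.2 uses that day to impute a date for patients not exposed, and naming the period cures the ambiguity.

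On posture, a sitting Visit 1 reading may exist, since 6.2.12 calls for one. The conflict is between texts, and mixing of postures is possible but not shown.

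The sizing is assumption-driven, its upper end is a corner case, and it covers one timepoint, whereas 12.7.4 tabulates any flag within a period. All of this stands and limits the point to descriptive tables.

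**Conclusion.** The point holds in a limited form. SAP 10.2 departs from Protocol 13.4 and 13.6.6 on the clinic-safety baseline, and Table 6.2-1 does not say so. Followed literally, it carries persistent Period 1 changes into the Period 2 arm for vital signs and C-SSRS, in tables the addendum keeps.

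No efficacy inference is affected: the efficacy paragraph of 10.2 retains the period baseline. A drift common to both sequences cancels from the arm difference, though not from arm means or individual flags. The effect on flag rates is small: about 0.09% against 0.36% for the low-SBP flag at one timepoint under central assumptions, and at most about 4 discordant patients among 170 planned completers at the edge of the assumed range. Fewer are expected, since enrolment stopped before the planned number was reached.

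The orthostatic flags in 12.2.3 are wrong as written, and the posture statements need reconciling. The addendum does not name baseline characteristics, weight or oral mucosa, so those tables may not be produced.

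**What to change.** 1. In SAP 10.2, define the clinic-safety baseline as the last value before the first dose of each treatment period for measures taken pre-dose at Visit 6: vital signs (including the Appendix 6 change criteria), C-SSRS, weight and oral mucosa. If the reference-day fallback is kept, name the period it refers to. Align 10.23, 12.7.4, 12.7.5.1 and 12.7.5.3 with this.
2. Keep Screening as baseline for laboratory data and ECG, and list it in Table 6.2-1 as a departure from Protocol 13.4, with the reason.
3. Reconcile Protocol 9.2.10 with exclusion 6.2.12 and SAP 12.7.4 on posture at Visit 1. If no sitting Visit 1 reading exists, compute the follow-up vital-sign change from the sitting Day 1 H0 reading.
4. In SAP 12.2.3, change the flags to ≥ +20 (SBP) and ≥ +10 (DBP), matching the supine-minus-standing definition and the hypotension item in the same list.
5. Minor: remove the Day 21 weight change from 12.7.5.1.

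The cost is SAP wording, reconciliation of the posture text and programming. The values needed for the period-level baseline are already scheduled at Visit 6, so no new assessment is required.
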